Improved quality of care by providing evidence based information to patients (parents) and reduced unwanted side effects in children. If on the other hand the trial did demonstrate effectiveness and cost-effectiveness in some subgroups but not others, and this was demonstrated to be cost-effective, then there is still likely to be considerable scope for better targeting of antibiotics, and limiting antibiotic use.

In addition to assessing effects of antibiotic treatment in children it is also highly relevant to be able to assess disease severity and risk for complications. Apart from improving indications for antibiotic treatment, heterogeneity of disease severity is also important because of monitoring and if needed referring patients and informing them and their caregivers. Both diagnostic studies to detect relevant severe disease, most importantly pneumonia, and assessing risks for complications incorporating standardised registration of patient characteristics and additional tests are lacking. Therefore we are aiming to also perform an observational study along the trial described above to develop prediction models that are both feasible in daily practice and could enhance detection of relevant infections in children that warrant special attention from primary care professionals.

### 3.1. Why is research needed now?

Antibiotics may be indicated in a child with acute cough but there is currently no evidence to support targeting antibiotics for common presentations. Therefore it is not surprising that prescribing decisions are made by doctors using traditional but non-evidence based clinical signs (e.g. sputum production, fever, chest signs, being unwell) as indications for antibiotic use. Among 430 children in our ongoing 3C PRIME (27) observational study of acute infective cough the key drivers for antibiotic prescription are: rhonchi on examination (among 40% of children), and symptoms of productive cough ('wet cough/rattly chest/sputum'), breathlessness, audible wheeze and fever, which are present in between 30% and 65% of children presenting with chest infections. A trial simply powered to estimate the average effect of antibiotics would provide unconvincing evidence to persuade doctors not to prescribe, as doctors tend to prescribe in the face of uncertainty and give patients the 'benefit of the doubt'. Thus it is necessary to study the heterogeneity of these children with acute cough and explore whether clinical and pathophysiological determinants identify subgroups where antibiotic treatment is or is not effective. The costs involved in children with acute bronchitis also differ from those in adults, because parents or care takers are also involved, with associated productivity losses, both in paid and unpaid work, and the enormous potential costs of future antibiotic resistance are often not included in estimates of cost effectiveness. (28)

Research is particularly needed now as antibiotic resistance is a major national and international priority and has been identified as one of the key public health threats of our time in high profile reports. The urgency of providing evidence now is also highlighted by the fact that primary care prescribing has been increasing again for several years, and clear evidence is needed to inform the more rational use of antibiotics in primary care, particularly for one of the commonest illnesses in children.

### 4. AIMS AND OBJECTIVES

Our aim is to provide evidence to inform the management of chest infections in children. The objectives are:

- To estimate the effectiveness of amoxicillin overall and in key clinical subgroups of children presenting with uncomplicated (non-pneumonic) lower respiratory tract infection in primary care.
- To estimate the cost-effectiveness of antibiotics overall and in key clinical subgroups of children presenting with uncomplicated lower respiratory tract infection in primary care.
- To explore the estimates of effectiveness according to key pathophysiological subgroups (the presence of bacterial pathogens; raised C reactive protein measurement or white cell count; the presence of clinically undetected consolidation on X ray; oximetry; lung function).
- To develop prediction models to detect pneumonia in children and children at risk for complications (abnormal course of disease, hospital referral)

## 5. RESEARCH PLAN

This is a randomised placebo controlled parallel group trial of amoxicillin or placebo for children presenting with chest infections in primary care. The trial is nested within an observational study where the same measures and outcomes will be collected.

As agreed with the funder, a pilot phase will be carried out to assess the feasibility of this trial during the initial 6-7 months of the study. This will only involve the lead centre (Southampton) and between 5 and 10 GP practices and District General Hospitals each recruiting between 6 and 8 patients. For the pilot phase, the target is to recruit 30 participants in each group with a minimum of 15 participants in each.

### 5.1. Health Technologies being assessed

Main phase: Amoxicillin 50mg/kg in divided doses for 7 days.

### 5.2. Target Population

Children with chest infections (acute lower respiratory tract infection)

### 5.3. Recruitment

Recruitment will take place in Primary care, since this is where the vast majority of those presenting with acute Lower Respiratory Tract (LRTI) are managed. Table 1 (Appendix D) shows the process for recruitment for those children presenting to their healthcare provider with acute LRTI. Eligible patients

will be informed about the study by the consulting clinician or other staff at the General Medical Practice or Hospital, who will explain the study and provide the patient with a patient information leaflet.

Recruiting sites will be provided with promotional study materials such as posters, short version participant information leaflets and interest cards to display and/or hand out, allowing the patients an opportunity to find out more about the study and consider participation.

## 5.4. Inclusion criteria

Children between 6 months and twelve years old presenting with an acute lower respiratory infection (LRTI), defined as an acute cough as the predominant symptom, judged by the doctor or Nurse Practitioner to be infective in origin, lasting <21 days, and with other symptoms or signs localising to the lower tract (sputum). (2, 15, 16) These inclusion criteria are not only very similar to the clinical criteria used in daily practice to diagnose acute bronchitis (29) but are also among the drivers of prescribing from our ongoing observational studies in children. (30, 31). This would mean the inclusion of at least one other symptom suggesting infection (a systemic infection (fever, raised temperature), coryza, wheezing, sore throat, earache). Children with previously diagnosed asthma presenting with acute respiratory symptoms felt by their doctor to be due to an acute infection and in whom antibiotics are being considered are eligible for randomisation, with additional anti-asthma treatment (e.g. increased bronchodilators or corticosteroids) also provided according to clinical need as assessed by the treating clinician.

## 5.5. Exclusion criteria

Exclude if:

- The cough is judged by the clinician to have a non-infectious aetiology (e.g. hayfever or asthma where there is no clear infective precipitant) or almost certain viral aetiology (croup, where antibiotics are not commonly prescribed. This includes where exacerbations of asthma are the clear and prominent cause of the cough/bronchoconstriction);
- Suspected *Bordetella pertussis*;
- Severe tachypnoea as judged by the recruiting clinician
- immune-compromised;
- antibiotic use in previous 30 days;
- Children with asthma whose presentation is felt to be due to a non-infective asthma exacerbation and in whom antibiotics are not being considered eligible, nor children without a previous diagnosis of asthma in whom the presentation is suggestive of asthma rather than an infection (as per national asthma guidelines, e.g a less acute history, predominant wheeze, breathlessness, reduced peak expiratory flow rate, asthma risk factors).

For the trial but **not the observational study**— also exclude:

- Children with hypersensitivity to any of the penicillins should also be excluded or to any of the excipients (see section 6).
- History of a severe immediate hypersensitivity reaction (e.g. anaphylaxis) to another beta-lactam agent (e.g. a cephalosporin, carbapenem or monobactam).
- History of jaundice/hepatic impairment due to amoxicillin.
- Children who are on concomitant medication which, based on the clinical judgment of the clinician, may lead to clinically significant interaction with amoxicillin.
- Children with known severe renal failure, hepatic failure, infectious mononucleosis (active or within last two months), or phenylketonuria.
- Children currently taking any medications known to interact with amoxicillin (e.g. probenecid, sulfapyrazone, methotrexate, mycophenolate, oral anticoagulants) or increase the risk of adverse reactions (e.g. allopurinol).
- If a sibling living in the same household is already enrolled on the trial taking project medication
- Suspected pneumonia based on clinical examination (oxygen saturation below 92% or focal rales) or being very severely ill as judged by the doctor.
- Children previously entered into the ARTIC PC trial.
- Children who have been involved in another medicinal trial within the last 90 days.
- The criteria for referral to hospital using the NICE Feverish Children Clinical Guideline 160 and NICE guideline on Sepsis in Children and Adults. (32)
- individuals with very severe, oral steroid-dependent asthma who may be at greater risk of serious infection .

The age range was chosen because the prevalence of chest infections and the use of antibiotics is high in this group, and the children are more likely to be homogeneous regarding body composition, pharmacology and aetiology of respiratory tract infections. Children younger than 6 months are more likely to have immature immune responses and signs of a severe infection are more likely to be non-specific, and older children between 12 and 18 are more comparable to adults than the school children regarding body composition.

## 5.6. Consent

The legal guardian of the child will be asked to consent to the study after they have considered a patient information leaflet about the study (approved by an NHS Multi-Centre ethics committee) and had sufficient time to consider participation and ask questions. For those children who are able to understand the study, they will also be asked to consider an age appropriate patient information leaflet and ask questions about participation before also signing an age appropriate assent form. If necessary, clinicians will see other patients in order to allow sufficient time for patients to read materials and formulate questions. All legal guardians will be asked, at the time of consent, to complete a 'consent to contact form' with a preferred method of contact for follow up at day 2 by study staff and to be able to be contacted if they have opted to an x-ray (see 5.11. Data Collection - Measurements and follow-up).

## 5.7. Intervention

Pilot phase: As in the main trial we will use amoxicillin. The pilot is to test the acceptability of taking a placebo and test the study paperwork for both parents and recruiting clinicians.

Main phase: Weight related dosing is likely to provide the best evidence of effectiveness, and the best evidence to convince prescribers of the lack of effectiveness of antibiotics, since the alternative, the current BNF guidance using fixed doses, has broad categories of dosing according to age, and doses are particularly low for children in the higher end of the age ranges.

General Practitioners will specify the number of Milliliters (mls) of syrup to be taken three times per day using medicine syringes, based on a weight measurement of the child in light clothing taken during the consultation. We anticipate the easiest way to operationalise the dosing and avoid errors is to provide doctors with dosing schedules according to deciles of weight. Amoxicillin is the first choice antibiotic in LRTI and with current levels of intermediate resistance should cover most organisms. (10) The rationale for the dose (Amoxicillin 50mg/kg/24 hours (in divided doses) is in line with guidance from the BNF for children, and is supported by a Monte Carlo simulation to reach a Minimal Inhibitory Concentration (MIC) of around 1.5 - to cover *H. influenzae* as well as intermediate resistant *Pneumococci* for 90% of the intended population. (10) We estimate that no fewer than 5 days above the MIC is needed to achieve bacterial eradication. However, a 7 day course is more in line with current practice and so has been chosen on pragmatic grounds to allow not only for poorer compliance, but also for greater acceptability to clinicians (similar consensus was required for the previous similar trial in adults):(10) it is imperative that the intervention, and hence the results of the trial, are seen by clinicians (and parents) as providing a rigorous test of antibiotics with a sufficient dose and duration to conclusively estimate effectiveness.

In both arms, parents of the children will have trial medication and also be allowed to use self-medication *ad libitum* (paracetamol or ibuprofen). All parents will be instructed to seek medical assistance again in the event that symptoms progress.

## 5.8. Randomisation

Parents and children who consent to the study and agree to randomization will receive either antibiotic or placebo. The clinician will dispense sequentially numbered pre-prepared randomised packs. The randomisation codes for antibiotic or placebo will be kept by the manufacturer and with a dedicated unblinding service. Unblinding can occur if requested by clinicians for clinical reasons – for example where adverse events occurred (e.g. anaphylaxis, admission to hospital with life threatening illness (e.g. septicaemia; meningitis; severe pneumonia requiring ICU admission) and death.)

## 5.9. Pilot phase

As agreed with the funder, an internal pilot phase will be carried out to assess the feasibility of this trial during the initial 6-7 months of the study. This will only involve the lead centre (Southampton) and between 5 and 10 GP practices and or Hospitals each recruiting between 6 and 8 patients. For the pilot phase, the target is to recruit 30 participants in each group with a minimum of 15 participants in each.

## 5.10. Observational study for those refusing randomisation

Some parents will decline randomisation, due either to concern about getting antibiotics or not getting antibiotics. The main concern for the trial data is that due to selection bias the trial may end up addressing the milder end of the clinical spectrum. Hence we propose, as in our adult trial, (10) that those not consenting to randomisation are offered participation in an observational study where the same outcomes are collected so that the characteristics and outcomes can be compared with trial participants. We have allowed for up to 30% additional parents being willing to undertake the observational trial.

Observational study to develop prediction models;

In all patients included in the trial and observational study we will analyse the relations between patient characteristics and results of additional tests and on the other side the presence of pneumonia and the occurrence of complications.

## 5.11. Data Collection - Measurements and follow-up

This study is a randomised clinical trial during which clinical assessment as well as additional measurements regarding aetiology and disease severity will be made and related to the effects of treatment. The recruiting clinician will complete a Case Report Form (CRF) of comorbidities, clinical signs and the severity of baseline symptoms reported by the patient (rating each symptom 'no problem', 'mild problem', a 'moderate problem', or 'severe problem'). (10) Co-morbidity and respiratory tract infections in the previous year will also be documented. The data will be entered onto a secure, password protected, study specific database hosted by the Clinical trials Unit (CTU) see 10.3. Data Recording and Record Keeping page 39.

In addition a capillary blood sample and a single sweep dual viral/bacterial throat swab will be taken (we will use the same technique which has proven both very acceptable and with high yields in the TARGET cohort), and pulse-oximetry will be performed. Sampling will be optional to maximise the generalisability of the sample, but we envisage from our experience of the TARGET cohort and other studies a high level of acceptance of sampling (at least 80%). The key microbiology of interest is the bacteriology for the common bacterial pathogens since we are interested in exploring whether the presence of pathogens predicts response to antibiotics (funded in this application) but we will also analyse the viral samples. With consent we will store samples for future analysis in a UK approved and Registered Biobank.

In the first week after inclusion, a chest x-ray will also be performed among willing participants. The study team will contact them with an appointment for the x-ray in a hospital close to their home. A standard x-ray request form will be used by all sites that will be supported by a Standard Operating Procedure detailing the reporting mechanism required for the study. This SOP will include both the timelines for images to be taken and definitions of the commonly seen conditions and when the requesting clinician should be informed of the outcome of the imaging. Any out of pocket expenses for attending the x-ray will be reimbursed.

The parents will keep a diary of symptoms and daily activities (including days away from work of parents) for at least one week and after that as long as symptoms persist up to four weeks after inclusion. All patients will be followed at 1 month when medication bottles will be returned and the symptoms diaries collected, and among willing participants over 6 years of age a forced-expiratory volume test will be done before and after administration of Salbutamol. This will allow some exploration of whether there is any difference in effectiveness among those with evidence of reversible airways obstruction. Parents/ guardians will be asked to guess individual treatment assignments (amoxicillin, placebo or don't know) and provide reasons for guesses on day 2 when as part of the telephone follow up before any evidence or side effects.

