### 1.7. Baseline measures

Structured history/examination; pulse oximetry; optional x-ray (for clinically undetected consolidation); and optional samples: swabs (for microbiology) and pinprick blood sample (for CRP and Full blood count). The x-ray will take place in a facility with suitably trained staff and safety measures local to the recruiting site with the site being responsible for the optional samples.

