## 1.8. Measurement of costs/outcomes

Primary outcome: duration of moderately bad symptoms (from validated symptom diary). Secondary outcomes: symptom severity (days 2-4); duration of symptoms until very little problem; the development of new or worsening symptoms; complications. Health related quality of life will be measured by proxy methods in which The EuroQoL (EQ5DY) will be completed by patients or carers for age older than 7, children will complete the questionnaire separately too on days 0,1,3, 7, 14 21 and 28. Follow-up (at 1 month): measure lung function (if aged 6+).

Outcome parameters for observational study: development of new or worsening symptoms; complications, diagnosis of pneumonia based on chest X-ray.

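### Lung function at 1 month and chest X-rays taken during the treatment week are planned as effect modifiers, although both are measured after randomisation

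*Protocol*

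**What the plan says.** Section 4 has as its third objective "To explore the estimates of effectiveness according to key pathophysiological subgroups", and the list that follows includes "the presence of clinically undetected consolidation on X ray; oximetry; lung function". Sections 1.11 and 9.1 also name chest X-ray abnormalities among the potential effect modifiers to be explored.

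On lung function, Section 5.11 says: "All patients will be followed at 1 month when medication bottles will be returned and the symptoms diaries collected". At that visit, "among willing participants over 6 years of age a forced-expiratory volume test will be done before and after administration of Salbutamol". The stated purpose follows directly: "This will allow some exploration of whether there is any difference in effectiveness among those with evidence of reversible airways obstruction". Section 1.8 also places the test at 1 month, under the heading for costs and outcomes. The protocol describes no lung function test before randomisation.

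On the X-ray, Section 1.7 lists among the baseline measures an "optional x-ray (for clinically undetected consolidation"). Section 5.11 schedules it differently: "In the first week after inclusion, a chest x-ray will also be performed among willing participants", with the study team arranging a hospital appointment.

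Randomisation happens when the recruiting clinician hands over the next numbered pack (Section 5.8 and the dispensing part of Section 6.1). The course lasts 7 days (Section 5.1).

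**The concern.** A subgroup effect keeps the protection of randomisation when membership is fixed before treatment is assigned. Then the two arms within the subgroup differ only by chance. If membership is decided later, and treatment can alter it directly or through faster recovery, the arms within the subgroup need no longer be alike.

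Both markers are open to this. Lung function is measured when treatment has ended and the primary outcome has been observed. A film taken late in the first week may show a chest that several days of amoxicillin or placebo have already changed. Both tests are optional and require attendance after randomisation, so who is tested may also depend on how the child is doing.

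At stake is the reading of the objective on pathophysiological subgroups. An apparent lack of benefit in children with consolidation or reversible obstruction could come from how those groups were formed rather than from the drug.

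**Working it through.** The protocol gives no figure for this point, so none can be reproduced. The check sets timing against use and then illustrates the mechanism under stated assumptions.

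**Timing against use**

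| Marker | Measured | Treatment by then | Planned use |
|---|---|---|---|
| Five clinical subgroups (1.10) | Features of the presenting illness | Not started | Powered interactions |
| Chest X-ray (5.11) | First week after inclusion, by appointment | Overlaps the 7-day course | Subgroup or effect modifier (4, 1.11, 9.1) |
| Lung function (1.8, 5.11) | 1 month, willing children aged about 6 and over | Course complete, 28-day diary closing | Subgroup (4, 5.11) |

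Section 5.12 says the first 2 to 4 days are when antibiotics might make a difference. The X-ray window includes those days.

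**Illustration 1: hand arithmetic, all inputs assumed.** Among children with consolidation, half recover fast (4 days) and half slowly (10 days), and treatment has no effect on symptoms. By X-ray day the film has cleared in a proportion *c* of fast children and in no slow child. Among children still positive:

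- fast share *f* = 0.5(1 − *c*) / [0.5(1 − *c*) + 0.5]
- mean duration = 4*f* + 10(1 − *f*) = 10 − 6*f*

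Amoxicillin, *c* = 0.50: *f* = 0.25/0.75 = 0.333, mean 10 − 2.0 = 8.0 days.
Placebo, *c* = 0.20: *f* = 0.40/0.90 = 0.444, mean 10 − 2.67 = 7.33 days.
Spurious difference: 8.0 − 7.33 = 0.67 day against amoxicillin.

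The result depends on the assumptions. If *c* = 0.20 in both arms, the means are both 7.33 and the difference is 0. If slow children's films clear at the same rate as fast children's within each arm, *f* = 0.5 in both arms, both means are 7.0 and the difference is again 0. In this example the distortion needs clearance that differs by arm and is also related to prognosis.

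**Illustration 2: simulation, all inputs assumed.** 2,000,000 children have a latent severity *L* (standard normal). Recovery is exponential with daily hazard 0.15·exp(−0.7*L*), multiplied by the treatment hazard ratio (HR) in the drug arm and censored at 28 days. The log-odds of a positive marker are −1 + 1.5*L*. For the post-randomisation marker, the drug multiplies those odds by 1, 0.61 or 0.37. HRs are ratios of events per unit of follow-up time.

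| True HR | Odds factor | Post-randomisation marker: HR if positive / negative (ratio) | Baseline marker: HR if positive / negative (ratio) |
|---|---|---|---|
| 1.0 | 1 | 0.998 / 0.998 (1.000) | 1.002 / 0.996 (1.006) |
| 1.0 | 0.61 | 0.938 / 0.949 (0.988) | 0.999 / 1.001 (0.998) |
| 1.0 | 0.37 | 0.878 / 0.905 (0.971) | 1.001 / 1.001 (1.000) |
| 1.3 | 1 | 1.266 / 1.279 (0.990) | 1.264 / 1.283 (0.985) |
| 1.3 | 0.61 | 1.187 / 1.212 (0.979) | 1.266 / 1.282 (0.988) |
| 1.3 | 0.37 | 1.118 / 1.157 (0.967) | 1.270 / 1.285 (0.989) |

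With factor 0.37 and no true effect, 19.0% of the drug arm is marker-positive against 32.9% of the placebo arm, and mean severity among positives is 0.93 against 0.73. Milder children have moved from the positive to the negative stratum in the drug arm, so the drug looks worse in both strata. The ratio of the two stratum effects, which is the interaction, moves much less. With factor 1 there is no distortion.

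**The case against.** Several points on the other side are sound.

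- **Exploratory status.** Section 4 speaks of exploring, and Sections 1.11, 5.11 and 9.1 are equally cautious. The power calculation and the 1% level (Sections 5.15 and 9.3) belong to the five clinical subgroups. A reader might infer that the trial's main results are compromised; the documents do not support that.
- **No bias without an effect on the marker or attendance.** A reader might infer that the subgroup results must be wrong because the measurement is late. That does not follow. The protocol gives no effect of amoxicillin on film clearance or on reversibility at 1 month, and a stable trait would be little affected.
- **The size is assumed.** The 0.67-day figure is not an estimate for this trial. It also lies well under the 3-day difference that Section 5.15 treats as worthwhile. The planned interaction terms were less distorted than the stratum effects in the simulation.
- **Clinical weight.** A reader might suppose that X-ray-positive children are the group prescribers care about most. Sections 3 and 3.1 name other drivers of prescribing: chest signs, productive cough, breathlessness, wheeze and fever. Consolidation that is clinically undetected is by definition not known at the consultation.
- **Delegation.** Section 5.11 leaves X-ray timelines to an SOP, and Section 9.1 says subgroups will be finalised blind to allocation. The contents of the Appendix D schedule could not be read here.

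The last point does not dispose of the matter. Blind specification does not change when a marker was measured. An SOP working within a first-week window does not turn the film into a baseline measure. No analysis plan can supply a pre-randomisation lung function test that was not done. The two parts are not equally strong: the lung-function part is firm, while the X-ray part depends on when films are actually taken.

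**Conclusion.** The point holds as a limited one. The protocol plans to explore effectiveness by lung function measured after treatment and at the end of the primary outcome period, and by an X-ray that it calls baseline but schedules during treatment. Effects within such subgroups lack the protection of randomisation and may be biased if treatment affects the marker or attendance.

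The documents do not allow the size to be stated. Under the assumptions shown, a true HR of 1.0 appeared as 0.88 to 0.95 within strata and a true HR of 1.3 as 1.12 to 1.21, against about 1.26 to 1.29 with a baseline marker. There was no distortion when treatment left the marker alone. The overall comparison and the five powered subgroups are unaffected.

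**What to change.** **Lung function.** Remove it from the effect-modifier list in Section 4, and delete the sentence in Section 5.11 that gives it that purpose. Report 1-month lung function by arm as a follow-up outcome. For the airway-obstruction question, use features recorded at baseline, such as wheeze (already within the chest-signs subgroup of Section 1.10) or previously diagnosed asthma (co-morbidity is recorded under Section 5.11).

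**X-ray.** Reconcile Section 1.7 with Section 5.11 on whether the film is a baseline measure. Record the interval from first dose to film for every child X-rayed. Describe the X-ray interaction as an exploratory post-randomisation analysis, show X-ray findings by arm, and pre-specify a sensitivity analysis limited to pre-dose or earliest films. Only pre-dose films are free of any influence of the drug on the film; a limit of a day or two after the first dose reduces the problem without removing it.

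**Cost.** Wording changes and one recorded interval. The reversibility subgroup is lost, and the restricted X-ray analysis has less precision.
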